4.0 LIST OF ABBREVIATIONS AND DEFINITIONS OF TERMS

Term	Definition
A β	amyloid β
AChE	Acetylcholinesterase
AChEI	Acetylcholinesterase Inhibitor
AD	Alzheimer's Disease
ADAS-Cog	Alzheimer's Disease Assessment Scale Cognitive Subscale
ADCS-ADL	Alzheimer's Disease Cooperative Study Activities of Daily Living Inventory
ADL	Activities of Daily Living
ADNI	Alzheimer's Disease Neuroimaging Initiative
AE	Adverse Event
ALT	Alanine aminotransferase (SGPT)
ANCOVA	Analysis of Covariance
APaT	All-Patients-as-Treated
APOE	Apolipoprotein E
APP	Amyloid Precursor Protein
AREDS	Age-Related Eye Disease Study
AST	Aspartate aminotransferase (SGOT)
BACE	β -site APP cleaving enzyme
BP	Blood Pressure
β hCG	β -Human Chorionic Gonadotropin
BSA	Body Surface Area
BUN	Blood Urea Nitrogen
CAM	Confusion Assessment Method
CBC	Complete Blood Count
CDR-SB	Clinical Dementia Rating Sum of Boxes
CDT	Counterfeit, Diversion and Tampering
CFR	Code of Federal Regulations
CI	Confidence Interval
cLDA	Constrained Longitudinal Data Analysis
CMH	Cochran-Mantel-Haenzel
CMV	Cytomegalovirus
CRF	Case Report Form
CRO	Clinical Research Organization
CSF	Cerebrospinal Fluid
CSR	Clinical Study Report
CTD	Clinical Trial Directive
CYP	Cytochrome P450
DNA	Deoxyribonucleic Acid
DMC	Data Monitoring Committee
DRESS	Drug Reaction with Eosinophilia and Systemic Symptoms
DSM-IV-TR	Diagnostic and Statistical Manual of Mental Disorders, 4th Edition, Text Revision
EBV	Epstein-Barr Virus
ECG	Electrocardiogram
ECI	Events of Clinical Interest

Term	Definition
eCRF	Electronic Case Report Form
EDC	Electronic Data Capture
eDMC	External (to Sponsor) Data Monitoring Committee
EDTA	Ethylenediamine Tetraacetic Acid
EIA	Enzyme immunoassay
EM	Exposure Multiples
EMA	European Medicines Agency
EQ-5D	EuroQol Five Dimension Questionnaire
EOC	Executive Oversight Committee
ETDRS	Early Treatment Diabetic Retinopathy Study
EU	European Union
FAF	Fundus Autofluorescence
FAS	Full Analysis Set
FDA	Food and Drug Administration, USA
FSH	Follicle Stimulating Hormone
FTA-ABS	Fluorescent treponemal antibody absorption
GCP	Good Clinical Practice
GMP	Good Manufacturing Practice
HEA	Health Economic Assessment
HLA	Human Leukocyte Antigen
ICF	Informed Consent Form
ICH	International Conference on Harmonisation of Technical Requirements for Registration of Pharmaceuticals for Human Use
ICMJE	International Committee of Medical Journal Editors
ID	Identification
IEC	Independent Ethics Committee
IMP	Investigational Medicinal Product
IND	Investigational New Drug Application; legal instrument in the USA that allows trial of unapproved, investigational new drugs in human subjects
Investigational Product	The drug, biologic, and/or device being investigated in the current trial
IPR	Indirect Pharmacologic Response
IRB	Institutional Review Board
IU	International Units
IVRS	Interactive Voice Response System
K_i	Equilibrium Inhibition Constant
K-M	Kaplan-Meier
LDH	Lactate Dehydrogenase
LFT	Liver Function Test
LSM	Least Squares Mean
MAR	Missing at Random
MCAR	Missing Completely at Random
MFAS	Modified Full Analysis Set
MMSE	Mini-Mental State Examination
MNAR	Missing Not at Random
MRI	Magnetic Resonance Imaging

Term	Definition
mSv	millisievert
NINCDS-ADRDA	National Institute of Neurological and Communicative Diseases and Stroke/Alzheimer's Disease and Related Disorders Association
NMDA	N-Methyl-D-Aspartate
NPI	Neuropsychiatric Inventory
PD	Pharmacodynamic
PDLC	Pre-Defined Limit of Change
PET	Positron Emission Tomography
PiB	Pittsburgh compound B
P-gp	P-glycoprotein
PK	Pharmacokinetic
PK/PD	Pharmacokinetic/Pharmacodynamic
p-tau	Phosphorylated Microtubule-Associated Protein Tau
RBC	Red Blood Cell
RNA	Ribonucleic Acid
RPE	Retinal Pigment Epithelium
RSD	Rising Single Dose
RSI	Reference Safety Information
RUD Lite	Resource Utilization in Dementia Lite Questionnaire
SAE	Serious Adverse Event
(S)AE	All adverse events, including serious adverse events
SAP	Statistical Analysis Plan
sAPP β	N-terminal fragment secreted after β -secretase cleavage of APP
SGOT	Serum Glutamic Oxaloacetic Transaminase (AST)
SGPT	Serum Glutamic Pyruvic Transaminase (ALT)
siDMC	Standing Internal (to Sponsor) Data Monitoring Committee
SOC	System Organ Class
T-BIL	Total Bilirubin
TC	Telephone Contact
Term	Termination
THV	Total hippocampal volume
TSH	Thyroid Stimulating Hormone
Tx	Treatment
UGT1A1	Uridine diphosphate glucuronosyltransferase 1A1
ULN	Upper Limit of Normal
Unsched	Unscheduled
USA	United States of America
WBC	White Blood Cell

5.0 INTRODUCTION

5.1 Therapeutic Rationale

Alzheimer's disease (AD) is a slowly developing neurodegenerative disease that is the leading cause of dementia world-wide. Currently available treatments for AD are limited, and include cholinesterase inhibitors (eg, donepezil) and the low affinity NMDA receptor antagonist (memantine) which modestly improve symptoms but do not alter disease progression. Therefore, novel pharmacological agents that slow or halt the progression of AD are needed.

Alzheimer's disease is characterized by specific histopathological features including amyloid deposits (plaques), neurofibrillary tangles, and neuronal degeneration. The "amyloid hypothesis" posits that amyloid- β ($A\beta$) peptides aggregate into complexes, such as fibrils and plaques, which subsequently trigger the development of tau-related neurofibrillary tangles. These tangles are thought to be the more proximal cause of neuronal degeneration. $A\beta$ pathology appears to begin years before the onset of AD and is thought at some point to trigger tau pathology, neural degeneration, and the subsequent gradual emergence of clinical symptoms. As amyloid plaques continue to accumulate, tangle pathology spreads to a variety of brain regions, leading to progressive neuronal degeneration, brain atrophy, and cognitive decline.

$A\beta$ peptides are produced when amyloid precursor protein (APP) is cleaved by three distinct proteases: α -secretase, BACE1 (β site APP cleaving enzyme 1; also known as β -secretase), and γ -secretase. Most APP is processed by α and γ -secretases to generate nonamyloidogenic peptides. However, 5-10% of APP is cleaved by BACE1 and γ -secretase to generate pathogenic $A\beta$ peptides ($A\beta_{40}$ and $A\beta_{42}$). Deletion of BACE1 in mice eliminates $A\beta$ in both the plasma and the brain. Thus, inhibition of BACE1 is a potential therapeutic strategy for slowing or halting progression of AD.

MK-8931 is a potent BACE1 inhibitor being developed for the treatment of AD. It has been shown to reduce $A\beta$ levels in the cerebrospinal fluid (CSF) and brain of rodents and primates. MK-8931 also reduces $A\beta$ in human CSF. In Phase 1 trials, MK-8931 has been generally safe and well tolerated (see Investigator's Brochure). These results suggest that MK-8931 may reduce $A\beta$ production in humans and could potentially slow progression in subjects with mild to moderate AD. Detailed information about MK-8931 including preclinical studies, pharmacokinetics and other relevant information is provided in the Investigator's Brochure.

5.2 Subject Population Rationale

This long term safety trial will start with enrollment of the first subject who completes the initial 78 week trial and will end when the drug either becomes commercially available or when the MK-8931 program is terminated.

Subjects may start or switch to another cholinesterase inhibitor or memantine during this trial. Other additional treatments must not be initiated during the trial except as otherwise specified in this protocol.

Details about specific benefits and risks for subjects participating in this clinical trial can be found in the accompanying Investigator's Brochure and Informed Consent documents.

5.3 Trial Design Rationale

This is a parallel group, multi-site, double-blind, long term safety trial to provide access to MK-8931 before it is commercially available, to estimate the effects of delayed start of MK-8931, and to evaluate the safety and tolerability of two doses of MK-8931 in the extended treatment of mild to moderate AD. MK-8931 is hypothesized to exert disease modifying effects in subjects with AD. A delayed-start design may provide supportive evidence of disease modification in AD if the treatment effect is sustained and greater in the group of subjects that starts the active treatment earlier as compared to the group of subjects with a substantial delay in the start of active treatment. Results from the long term safety trial will also provide data regarding the sample sizes necessary for, and the feasibility of, delayed start studies with disease modifying therapeutics for AD. In addition, this long term safety trial will be used to further assess the long term effects of MK-8931 on disease progression, health economic effects, and the safety and tolerability of MK-8931. Some Sponsor personnel will be unblinded following the completion of the initial 78-week trial. Some Sponsor personnel will remain blinded during the long-term trial, as necessary, for the conduct and collection of efficacy data, including the 24-month timepoint to support the primary objective regarding efficacy. Details are included in the Sponsor's blinding document.

Once a subject enters the long term safety trial, participation will continue until one of the following occurs: 1) MK-8931's development is terminated for mild to moderate AD (eg. due to a lack of efficacy), 2) MK-8931 is approved by regulatory agencies and becomes commercially available, 3) the subject voluntarily withdraws or 4) the subject is discontinued for safety reasons. The long term safety trial is expected to continue up to five years after the first subject enters the trial.

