7.7.1.2 Exploratory Efficacy Endpoints

The exploratory efficacy endpoints are:

1. the change-from-Baseline score in the ADAS-Cog (at all scheduled timepoints with the exception of Week 104),
2. the change-from-Baseline score in the ADCS-ADL (all scheduled timepoints with the exception of Week 104)
3. the change-from-Baseline score in the CDR-SB (all scheduled timepoints).
4. the change-from-Baseline score in the MMSE (all scheduled timepoints)
5. the change-from-Baseline score in the NPI (all scheduled timepoints)
6. the Health Economics and Quality of Life Endpoints

7. the Pharmacogenetic Analyses Safety Monitoring and Assessments

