8.2.1 Primary Efficacy Analysis

The primary efficacy endpoints are the change from Baseline (CFB) in ADAS-cog score and the change from Baseline in ADCS-ADL score at Week 104 (Visit 13).

A delayed start design will be used to support the potential disease modifying effect of MK-8931 by comparing the 40mg/40mg arm to the Pbo/40mg arm. However, due to increased variance and anticipated dropout rate over time, the study is not powered to demonstrate significance on these endpoints, even if significance was demonstrated at 18 months.

All available data from the initial 78-week trial will be utilized in the analyses, even that from subjects who do not continue into long term safety trial. It is possible that the 40 mg dose may be dropped for reasons due to safety, in which case all subjects would receive 12 mg. The primary comparison in this case would be between the 12 mg / 12 mg arm and the Pbo / 12 mg arm (with any subjects receiving 40 mg or 60 mg excluded from the analysis).

The primary analysis approach will be conducted separately on each of the endpoints.

A longitudinal ANCOVA model will be used on the change scores, with time treated as a categorical variable so as not to impose any restriction on the trajectory of the means over time. The analysis model will adjust for the categorical factors of geographic region (US/Canada, Europe/Australia/New Zealand, Japan, Rest of the World), treatment (one or two remaining dose[s] of MK-8931 or placebo), gender, APOE genotype (APOE 4 positive, APOE 4 negative), baseline use of Vitamin E (0-400 IU/day, > 400 IU/day), baseline AD medication (use of AChEI or memantine, no use of AChEI or memantine), study cohort from the initial 78-week trial (Safety Cohort, Main Cohort) and the interaction of time-by-treatment, with the baseline values of MMSE and age included as continuous covariates. The baseline value of the dependent variable, as well as the baseline-by-time interaction term will also be included. The Week-78 change-from-Baseline mean treatment differences (MK-8931 – placebo), corresponding confidence intervals (CIs), and P-values will be estimated from this model. An unstructured covariance matrix will be used to model the correlation among repeated measurements.

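### Section 5.3 requires a sustained early-start advantage, but section 8.2.1 plans no estimate of how the gap changes after the delayed start, and its estimation sentence names Week 78 instead of Week 104

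*Combined protocol and SAP*

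**What the plan says.** Section 5.3 (Trial Design Rationale) sets the condition for supportive evidence of disease modification: "if the treatment effect is sustained and greater in the group of subjects that starts the active treatment earlier", relative to the group with the delayed start. So the advantage must exist and must last.

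Section 8.2.1 (Primary Efficacy Analysis) puts the design to use "by comparing the 40mg/40mg arm to the Pbo/40mg arm". Sections 6.1, 7.7.1.1 and 8.2.1 all place the primary ADAS-Cog and ADCS-ADL endpoints at Week 104 (Visit 13). The model has "time treated as a categorical variable so as not to impose any restriction on the trajectory of the means over time", a time-by-treatment interaction and an unstructured covariance matrix, and "All available data from the initial 78-week trial will be utilized in the analyses". The sentence that names the output, however, reads "The Week-78 change-from-Baseline mean treatment differences", with CIs and P-values to follow. Week 104 is not mentioned there.

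Section 7.7.1.2 makes the other ADAS-Cog and ADCS-ADL visits exploratory endpoints. Section 8.2.3 promises basic summary statistics for exploratory endpoints and no supportive analyses. Section 8.2.2 states that there are no formal hypotheses and sets 97.51% CIs. Section 8.0 says that no separate SAP will be issued.

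**The concern.** A Week-104 difference in favour of 40/40 fits two different histories. The gap present at Week 78 may have held or widened after the placebo group started 40 mg, which is what section 5.3 asks for. Or it may have been larger at Week 78 and be closing as the delayed-start group catches up, as a symptomatic or waning effect would produce. The plan neither says how *sustained* will be judged nor prespecifies a quantity that bears on it.

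The week named in the estimation sentence is a separate defect. Read literally, 8.2.1 would deliver the comparison made before the delayed start and leave out the primary estimate.

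Timing adds to both. Some sponsor personnel are unblinded once the 78-week trial is complete (section 5.3), so a contrast chosen later could be chosen with the Week-78 result known.

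**Working it through.** **1. Inputs from the documents.** Table 6: ADAS-Cog Week-104 SD 14.97, correlation with baseline 0.65, Pbo/40 progression 7.45; ADCS-ADL 20.21, 0.61 and -11.73. Table 7 footnote: 570 per arm, dropout 30% at Week 78 and 45% at Week 104, alpha 0.0249. Hence n1 = 570 × 0.70 = 399 and n2 = 570 × 0.55 = 313.5 per arm. Alpha is taken as two-sided, in line with the 97.51% CIs, so the critical value is 2.243.

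**2. The plan's power figures.** No treatment difference is given, so Table 7 cannot be reproduced forwards. It can be inverted.

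- ADAS-Cog: adjusted SD = 14.97 × √(1 − 0.65²) = 11.38; SE = 11.38 × √(2/313.5) = 0.909; implied difference = (2.243 + 0.313) × 0.909 = 2.32, or 31.2% of 7.45.
- ADCS-ADL: adjusted SD = 20.21 × √(1 − 0.61²) = 16.01; SE = 1.279; implied difference = (2.243 + 0.646) × 1.279 = 3.70, or 31.5% of 11.73.

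The two endpoints imply nearly the same proportional effect, so the inversion is plausible.

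**3. What the Week-104 test can see.** Its power depends only on the Week-104 difference. For ADAS-Cog at 2.32:

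| Week-78 gap | Week-104 gap | Pattern | Week-104 power |
|---|---|---|---|
| 1.16 | 2.32 | widening | 62.3% |
| 2.32 | 2.32 | kept | 62.3% |
| 3.48 | 2.32 | one third lost | 62.3% |
| 4.64 | 2.32 | half lost | 62.3% |

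Table 7's joint success at both weeks (46.1% for both endpoints) does not separate these patterns either: two significant differences can still be shrinking.

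**4. Precision of D104 − D78.** Three inputs are assumed because the documents do not give them: Week-78 SD 12 to 14, baseline to Week-78 correlation 0.68 to 0.72, and baseline-adjusted Week-78/104 correlation r from 0.70 to 0.95. With monotone dropout, per arm:

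- V104 = s104² × [(1 − r²)/n2 + r²/n1]
- V78 = s78²/n1
- C = r × s78 × s104/n1
- SE = √[2 × (V104 + V78 − 2C)]

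Here s104 = 11.38. For Week-78 SD 14 and baseline correlation 0.70, s78 = 14 × √(1 − 0.70²) = 10.00.

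- r = 0.70: V104 = 0.370, V78 = 0.251, C = 0.200, SE = 0.66.
- r = 0.95: V104 = 0.333, V78 = 0.251, C = 0.271, SE = 0.29.

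Over the whole assumed range the SE is 0.29 to 0.67, so the 97.51% CI is about ±0.65 to ±1.50 (2.243 × SE).

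**5. What the contrast can see.** For a fall of 2.32 (4.64 to 2.32), z is 2.32/0.67 = 3.5 at worst, and power is about 89% to more than 99%. For a fall of 1.16, z is 1.16/0.67 = 1.7 to 1.16/0.29 = 4.0, so the lower end misses 2.243.

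**6. Why by-visit output is no substitute.** Dropping C, as a reader with two separate by-visit CIs would have to, gives an SE of about 1.0 to 1.1. That is 1.6 to 3.8 times the correct value.

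**The case against.** A reader might infer that the primary analysis yields only the Week-104 difference and so cannot tell a lasting gap from a closing one. The documents do not support that. The model has categorical time, time-by-treatment and all initial-trial data, so it gives a difference at every visit and could give the contrast. The exploratory objective (section 6.2) also plans comparisons at multiple time points, and the flow chart schedules both scales at Weeks 91 and 130 and later. What is missing is a prespecified estimate with its uncertainty, not the data.

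A reader might also infer that the plan would present a closing gap as evidence of disease modification. No such rule exists. Section 5.3 says only that the design may give supportive evidence, and its own condition argues against that use.

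Three further objections carry weight:

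- There are no formal hypotheses, and the plan admits low power at Week 104. A second gate would be out of place.
- A CI for the contrast that includes zero does not show that the effect was sustained. With Week-78 SD 11 to 14, adjusted correlation 0.7 to 0.9 and 313.5 per arm observed at both weeks, power to show that at least half the ADAS-Cog gap is kept, when it is truly unchanged, is only 26% to 41%. The one-half threshold is illustrative.
- The 4.64-point scenario is extreme: 4.64/7.45 = 62% of the whole 104-week progression in Table 6.

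These points limit how the contrast should be used. They do not supply a reading of *sustained*, and the wrong week stands whatever view is taken of the rest.

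**Conclusion.** The concern holds in a limited form. The plan makes persistence of the advantage a condition of its main interpretive claim but prespecifies nothing that measures persistence, although its model could. The estimation sentence in 8.2.1 names the wrong week for the primary endpoint.

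The contrast would show a large loss of effect reliably and a loss of 1.16 points only under the more favourable correlations. It may be inconclusive about retention.

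The figures rest on the assumed Week-78 SD and correlations, and on an effect size inverted from Table 7 using only subjects observed at Week 104. If the mixed model's Week-104 SE of 0.82 to 0.86 is used instead, the implied difference is 2.556 × 0.82 to 2.556 × 0.86, about 2.1 to 2.2. At r = 0.70, power to detect halving is then about 85% (2.20/0.67 = 3.3). The conclusion is unchanged. Since the claim is only supportive and no hypothesis is tested, the point is worth correcting but does not threaten the trial.

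**What to change.** In section 8.2.1:

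1. Reword the estimation sentence so that the Week-104 mean treatment differences, CIs and P-values are estimated, with the Week-78 differences reported as well.
2. For each primary endpoint add the model-based contrast D104 − D78 (40/40 against Pbo/40) with a 97.51% CI. Label it an estimate, not a formal test or a gate. State that *sustained* will be interpreted from this contrast together with the Week-104 difference.

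The cost is one estimate statement per endpoint and a few sentences, with no new data or visits. The downside is that the contrast may leave retention unresolved, and that a positive Week-104 result with a closing gap could no longer be described as sustained.

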5.4 Outcome Measures Rationale

The primary clinical measures in this trial are the Alzheimer's Disease Assessment Scale Cognitive subscale (ADAS-Cog) and the Alzheimer's Disease Cooperative Study Activities of Daily Living Inventory (ADCS-ADL). The ADAS-Cog is a measure of cognition while the ADCS-ADL is a measure of functional ability in activities of daily living. The measures are validated instruments that are acceptable to regulatory agencies, have been used previously in drug trials in this patient population, and can reliably detect clinically relevant changes in AD.

After the initiation of P017, the FDA issued guidance to Sponsors indicating that all trials with BACE1 inhibitors that are longer than two weeks in duration must include routine monitoring of skin. There have been observations in the literature that mice lacking the gene for BACE2 have reduced pigment [30]. In recently completed studies of MK-8931 in two pigmented species (mouse and rabbit), reduced hair pigment was observed within four weeks of treatment in all animals, which was reversible with cessation of treatment. On microscopic examination, normal skin histology was observed except for loss of pigmentation in the hair follicle/shaft. There was no loss of melanocytes. All phases of the hair cycle were present, and no inflammatory or degenerative changes in hair follicles, sebaceous glands, epidermis, or dermis were observed. In contrast to these observations in mouse and rabbit, no change in hair pigment or skin and retinal histology have been observed in monkeys treated for up to 9 months with MK-8931 at exposures 36-fold above those achieved at the highest dose of MK-8931 tested in P017 (60 mg). Furthermore, no adverse events of skin hypo- or depigmentation have been reported thus far in prior human trials of MK-8931.

A review of preclinical data and the FDA request with a panel of expert dermatologists indicated the overall risk to patients is minimal. The risk of vitiligo, with loss of dermal melanocytes, was seen as low. If vitiligo were observed, medical management was recommended without discontinuation of study medication, given that vitiligo is not associated with significant morbidity or mortality. Hypopigmentation was viewed as being a more likely finding with BACE inhibitor treatment, rather than vitiligo. Hypopigmentation by itself was also not seen as requiring discontinuation of study medication. Therefore, baseline and post-treatment dermatology assessments were added to this protocol to document the incidence of hypopigmentation, not to detect a significant safety risk. Patients will be informed of the risk of hypopigmentation and instructed to use sun screen in affected areas if exposed to sunlight. A long-term risk may be increased skin cancer due to sun damage to the skin. Incident cases of hypopigmentation should be referred to a specialist for appropriate diagnosis and treatment, if clinically indicated. If no difference is seen in the occurrence of hypopigmentation between the placebo and MK-8931 groups after 300 subjects/group are evaluated at six months in the MK-8931 program (P017 and P019), the eDMC may recommend the discontinuation of the routine skin examinations in a future amendment. Sites would continue to collect skin-related adverse events and refer subjects for further dermatologic evaluation as needed.

